## 5. Investigation Plan

The study is a prospective, multi-center, non-randomized study to evaluate the safety and performance of The Intrepid™ TMVR System in patients with severe, symptomatic mitral regurgitation, who are at high risk for conventional mitral valve surgery.

The pilot study (also referenced as early feasibility study) is a single arm study without concurrent controls. The results will be evaluated referencing historical literature for surgical mitral replacement, surgical mitral repair, and transcatheter mitral repair.

### 5.1 Study Population

#### 5.1.1 Inclusion Criteria

The inclusion criteria listed are from the CIP for the US. **Appendix 10.1** provides a side-by-side view of the enrollment criteria for the different geographies. The slight differences in the inclusion criteria do not change the patient population being studied.

The subject must meet ALL of the following criteria:

1. Severe mitral regurgitation (MR Grade 3-4+)

2. Symptomatic mitral regurgitation (New York Heart Association (NYHA) Class II-IV)
3. Deemed to be at high risk for conventional mitral valve surgery by the local heart team (including, at minimum, a cardiac surgeon, interventional cardiologist, and an echocardiologist)
4. Age  $\geq 18$  (years)
5. Native mitral valve geometry and size compatible with The Intrepid™ TMVR
6. No or minimal mitral valve calcification
7. Willing to sign Informed Consent for participation in the study and return for all required post-procedure follow-up visits

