## 5. Risk/Benefit Analysis

This pilot study will enroll only patients with severe, symptomatic mitral regurgitation, who are at high risk for conventional mitral valve surgery.

These high risk patients, nevertheless, require treatment. This less invasive TMVR procedure may provide an alternative mitral valve replacement for patients for whom conventional surgery is not an option.

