This Statistical Analysis Plan (SAP) has been designed to document, before data are analyzed, the rationale for the study design, and the planned analyses that will be included in study reports. Clinical Investigational Plan (CIP) 1403 was developed and used in multiple geographies. The same data collection case report forms (CRFs) and similar inclusion and exclusion criteria were utilized. This SAP is developed based on the following CIP Versions:

Geography	CIP Number	Current Version
United States (US)	1403	4.0 / 2019.10.15
Australia	1403	A3 16 Dec 2019
United Kingdom (UK)	1403	V2.0 16 Dec 2019
Finland	1403	V2.0 16 Dec 2019
Greece	1403	V2.0 16 Dec 2019

Denmark	1403	V2.0 16 Dec 2019
France	1403	F5 20 Sep 2021

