## 5.2 Patient Review Committee

Subjects will be screened prior to study entry to determine if they meet the Eligibility Criteria. Subjects who have signed an Informed Consent and fulfill the inclusion criteria and none of the exclusion criteria are eligible for enrollment.

A Patient Review Committee (PRC) will consist of cardiac surgery, interventional cardiology, and echocardiology representatives who are not participating investigators. The PRC will serve in an advisory capacity to Medtronic and will review potential patients' clinical and imaging data to help ensure appropriate patient selection across all sites.

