## 6. Determination of Sample Size

This study treats up to 95 subjects worldwide who require replacement of their native mitral valve because of severe, symptomatic mitral regurgitation, but are at high risk for conventional mitral valve surgery. The enrollment is capped at 70 in the US, 30 in Australia, and 20 in each of France, Denmark, Finland, Greece, and the UK. The geography-specific and overall sample sizes are not statistically derived, as this is not a hypothesis-driven study.

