#### 7.1.3 Analysis Sets

Four analysis sets are defined for this study. The primary analysis will be based on the Approved Subjects analysis set. Analysis sets used for each objective are defined in the corresponding objective section. All data collected from consented and approved subjects will be utilized in the analyses as appropriate.

- **Consented Subjects:** Includes all subjects who signed a study informed consent. Time zero begins on the date of informed consent.
- **Approved Subjects:** Includes consented subjects who are reviewed and approved for implant by the PRC. Time zero begins on the date of informed consent.
- **Attempted Implant (Safety):** Includes approved subjects who were reviewed and approved by the PRC and entered the procedure room with the intent to attempt a TMVR procedure. Time zero begins on the date of procedure. This analysis set will be used for evaluating all safety data and clinical outcomes (i.e., NYHA, 6 Minute Walk Test (6MWT), Minnesota Living with Heart Failure Questionnaire (MLHFQ)).
- **Implanted Subjects (Hemodynamic Performance):** Composed of all attempted implant subjects with a functioning Intrepid device implanted at the time of exiting procedure room. Time zero begins on the date of procedure. This analysis set will be used for evaluating the valve performance (i.e., hemodynamics or imaging data). If the Intrepid valve is explanted or has a reintervention, then only data collected up to time of explant or reintervention are included in analysis regarding valve function.

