## 10. Statistical Appendices

### 10.1 Comparison of Inclusion and Exclusion Criteria Across Geographies

Listed below are inclusion and exclusion criteria in the geography-specific CIPs. Criteria with variations are italicized.

	United States CIP-1403 Version 4.0 2019.10.15	Australia CIP-1403 Version A3 16Dec2019	Finland, Greece, United Kingdom, Denmark CIP-1403 Version 2.0 16Dec2019	France CIP-1403 Version F5 20SEP2021
Inclusion Criteria				
1	Severe mitral regurgitation (MR Grade 3-4+)	Severe mitral regurgitation (MR Grade 3-4+)	Severe mitral regurgitation (MR Grade 3-4+)	Severe mitral regurgitation (MR Grade 3-4+)
2	Symptomatic mitral regurgitation (NYHA Class II-IV)	Symptomatic mitral regurgitation (NYHA Class II-IV)	Symptomatic mitral regurgitation (NYHA Class II-IV)	Symptomatic mitral regurgitation (NYHA Class II-IV)
3	Deemed to be at high risk for conventional mitral valve surgery by the local heart team (including, at minimum, a cardiac surgeon, interventional cardiologist, and an echocardiologist)	Trans-apical access deemed feasible by the treating physician	Trans-apical access deemed feasible by the treating physician	Deemed to be at high risk for conventional mitral valve surgery [STS Score > 8 or EuroSCORE > 15, or by agreement by the local heart team (i.e., surgeon, cardiologist & anesthesiologist)]
4	Age ≥ 18	Age ≥ 18	Age ≥ 18	Age ≥ 18

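### The Pilot Study SAP says geographic differences in the inclusion criteria leave the population unchanged, but its own Appendix 10.1 lists high surgical risk as a requirement only for the US and France

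*Combined protocol and SAP*

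**What the plan says.** The point concerns only the trans-apical Pilot Study SAP, which pools subjects recruited under several geography-specific versions of CIP-1403.

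- **SAP 3** says of those versions: "The same data collection case report forms (CRFs) and similar inclusion and exclusion criteria were utilized".
- **SAP 5** describes the population as patients "who are at high risk for conventional mitral valve surgery", and says the single-arm results will be evaluated with reference to historical literature on surgical replacement, surgical repair and transcatheter repair. SAP 6 applies the same risk description to all subjects worldwide.
- **SAP 5.1.1** reproduces the US criteria, sends the reader to Appendix 10.1 for the other geographies, and concludes: "The slight differences in the inclusion criteria do not change the patient population being studied".
- **SAP 10.1, inclusion row 3**, has high surgical risk in the US column (local heart team judgement) and in the France column (STS score above 8, EuroSCORE above 15, or heart team agreement). In both the Australia column and the Finland/Greece/UK/Denmark column the row reads: "Trans-apical access deemed feasible by the treating physician".
- **SAP 6** sets the sizes, with up to 95 treated in total: "The enrollment is capped at 70 in the US, 30 in Australia, and 20 in each of France, Denmark, Finland, Greece, and the UK".

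**The concern.** Surgical risk and access feasibility are different attributes, and neither implies the other. High surgical risk is also part of how the SAP defines its population, so dropping it from the listed criteria in five of seven geographies is hard to call slight.

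What is at stake is interpretation. The study has no hypothesis test and no concurrent control, so its results gain meaning from the description of who was treated and from comparison with published series. If part of the pooled set was not selected for high surgical risk, the high-risk label may not fit that part.

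Baseline characteristics (SAP 7.6), the primary safety endpoint (SAP 7.9.1) and the death listing (SAP 7.10) are not specified by geography or criteria group. SAP 7.8 plans interim analyses for publication and for CE submission. A reader of the pooled results would not see how many subjects came under each set of criteria, or whether their baseline profiles differ.

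**Working it through.** **1. Row 3 side by side (Appendix 10.1)**

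| Geography | High surgical risk listed? | Enrolment cap (SAP 6) |
|---|---|---|
| US | Yes, heart team | 70 |
| France | Yes, score or heart team | 20 |
| Australia | No, trans-apical feasibility | 30 |
| Denmark, Finland, Greece, UK | No, trans-apical feasibility | 4 × 20 = 80 |

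The remaining inclusion and exclusion rows for the last two lines were read through, and none requires high surgical risk. Row 3 is legible in all four columns of the appendix, and the re-reading found it italicised there, which is the SAP's own mark for a variation. This does not look like a text-extraction fault.

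**2. How many subjects could be affected**

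The SAP gives no enrolment by geography and says its sample sizes are not statistically derived, so there is no figure to reproduce. The caps give bounds.

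- Sum of caps: 70 + 30 + 5 × 20 = 200, against an overall maximum of 95.
- With the listed criterion: 70 + 20 = 90.
- Without it: 30 + 80 = 110.
- If N = 95, the minimum without it is 95 − 90 = 5, and 5/95 = 5.3%. The caps alone set no useful upper limit, because 110 exceeds 95.
- If N = 95 and the US enrols 70, 25 remain. France can take 0 to 20 of them, leaving 5 to 25 for the other five geographies: 5/95 = 5.3% to 25/95 = 26.3%.
- If N is 90 or fewer, the minimum is 0.

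**3. What a descriptive split could show**

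The documents give no event rate. Taking 20% purely as an assumption, the Clopper-Pearson 95% intervals are:

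| Events / group size | 95% interval |
|---|---|
| 1/5 | 0.5% to 71.6% |
| 5/25 | 6.8% to 40.7% |
| 18/90 | 12.3% to 29.8% |

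The problem at the smallest size does not depend on that assumption. With 0 events in 5 the upper limit is 1 − 0.025^(1/5) = 1 − 0.478 = 52.2%. A group near 5 can support counts only.

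**The case against.** The strongest reply is that the listed rows are not the whole of each plan. Only the US CIP-1403 is in the file, and it states the restriction outside its criteria list too, in the Risk/Benefit Analysis: "This pilot study will enroll only patients with severe, symptomatic mitral regurgitation, who are at high risk for conventional mitral valve surgery". The other national plans may do the same, and SAP 6 itself calls the worldwide population high risk. This stands as a limit: the documents show an unsupported sentence, not a demonstrated change of population.

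Second, the PRC is a common selection step. The Approved Subjects set is defined thus: "Includes consented subjects who are reviewed and approved for implant by the PRC". The Attempted Implant and Implanted sets are drawn from it. The PRC's members are not investigators, they review candidates across all sites, and the US criterion has no numeric threshold either. This carries weight but does not close the gap. SAP 5.2 says "The PRC will serve in an advisory capacity to Medtronic", and nowhere says that the PRC applied a surgical-risk requirement where the national criteria had none.

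Third, there are no pass criteria, the literature comparison is narrative, the appendix discloses the difference, and individual case summaries go to the FDA (SAP 7.2). All true, and the reason no planned test or decision rule is affected. But case summaries to a regulator do not help a reader of pooled tables, and disclosure in an appendix does not make the 5.1.1 sentence correct.

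Fourth, a split of outcomes may be imprecise, and surgical risk may not have been scored. Both are fair, and both limit what the split can settle.

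**Conclusion.** The sentence in SAP 5.1.1 is wrong as written: the appendix it cites does not bear it out. High surgical risk is a listed requirement in two of seven geographies, while SAP 5 and 6 apply the label to all.

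The share of subjects involved is at least 5.3% if all 95 are treated, 5.3% to 26.3% if the US also fills its cap, and possibly zero if 90 or fewer are treated. These are bounds from the caps, not evidence of enrolment. The actual mix, and any effect on event rates, cannot be determined from the documents. Nor can it be said that lower-risk patients were enrolled, since the PRC or unseen parts of the other plans may have excluded them.

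This should be corrected before pooled results are described as high risk. It bears on description and interpretation, not on any test.

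**What to change.** 1. Replace the 5.1.1 sentence with wording such as: Among the criteria listed in Appendix 10.1, high surgical risk is required for the US and France; the other five geographies list trans-apical feasibility in that row.
2. State whether the PRC required high surgical risk in every geography. If it did, that supplies the missing support. If not, readers learn what the pooled label covers.
3. Beside the pooled results, report descriptively for US + France and for the other five geographies: enrolment counts; the SAP 7.6 baseline variables, adding a surgical risk score only if one was collected; the primary safety endpoint; and the number of deaths. Show counts only if a group is near 5.
4. Call the pooled results high risk only as far as the PRC statement and the baseline data support it.

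The cost is one corrected sentence, one statement and one descriptive split of data held on common CRFs; deaths need only a count from the listing already planned in SAP 7.10. Neither the US CIP-1403 screening list (section 4.1) nor SAP 7.6 names a surgical risk score, so the baseline comparison may have to rest on demographics, hemodynamics and medical history. The main drawback is wide intervals in a small group. No eligibility rule has to change.

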## 5.1.2 Exclusion Criteria

The exclusion criteria listed are from the CIP for the US. **Appendix 10.1** provides a side-by-side view of the enrollment criteria for the different geographies. The slight differences in the exclusion criteria do not change the patient population being studied.

The subject may not meet any of the following criteria:

1. Left ventricular ejection fraction (LVEF)  $< 20$  (%)
2. Evidence of intracardiac mass, thrombus, or vegetation
3. Pulmonary hypertension ( $> 70$  mmHg systolic)
4. Hypertrophic Obstructive Cardiomyopathy (HOCM)
5. Prior mitral valve surgery or endovascular procedure, any currently implanted mechanical prosthetic valve, or need for other valve surgery/procedure
6. Any endovascular therapeutic interventional or surgical procedure performed within 30 days prior to enrollment
7. Prior stroke within 30 days
8. Need for coronary revascularization
9. Need for emergent surgery
10. History of, or active, endocarditis
11. Gastrointestinal (GI) bleeding within 6 months
12. History of bleeding diathesis or coagulopathy or patient will refuse blood transfusion
13. Hemodynamic instability
14. Platelet count of  $<75,000$  cells/mm^3
15. Renal insufficiency (Creatinine  $> 2.5$  mg/dL)
16. Active infections requiring current antibiotic therapy (if temporary illness, patients may enroll 2 weeks after discontinuation of antibiotics)
17. Contraindication to transesophageal echocardiography (TEE)
18. Known hypersensitivity or contraindication to study or procedure medications/contrast which cannot be adequately managed medically

19. Pregnant, nursing or planning to be pregnant. (Female participants of childbearing potential must have a negative pregnancy test prior to enrollment)

## 5.2 Patient Review Committee

Subjects will be screened prior to study entry to determine if they meet the Eligibility Criteria. Subjects who have signed an Informed Consent and fulfill the inclusion criteria and none of the exclusion criteria are eligible for enrollment.

A Patient Review Committee (PRC) will consist of cardiac surgery, interventional cardiology, and echocardiology representatives who are not participating investigators. The PRC will serve in an advisory capacity to Medtronic and will review potential patients' clinical and imaging data to help ensure appropriate patient selection across all sites.

## 5.3 Clinical Events Committee and Data Safety Monitoring Board

The combined Clinical Events Committee (CEC) and Data Safety Monitoring Board (DSMB) will provide independent medical review and adjudication of adverse event data used in the safety assessment of the investigational device. The CEC will adjudicate all deaths, serious adverse events (SAEs), and safety endpoint events reported by the investigators. The CEC will follow the recommendations of the Mitral Valve Academic Research Consortium (MVARC) for classifying adverse events that relate to clinical safety endpoints.

A DSMB will assess interim study data and provide recommendations to Medtronic regarding study conduct, should they identify any issues that may affect the safety of the study subjects. The DSMB consists of a minimum of three members: 1) cardiologist with expertise in the management of mitral disease, 2) a cardiothoracic surgeon with expertise in mitral valve repair and replacement, and 3) a biostatistician. DSMB members are free from bias towards the study and independent from both the study and investigators and Medtronic.

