### 17.1.27 INTERACTION WITH NON-MITRAL VALVE INTRACARDIAC STRUCTURES

Interaction with non-mitral- valve intracardiac structures will be classified as

- Left ventricular outflow tract obstruction:
  - Visual narrowing of the LVOT tract AND
  - Peak LVOT jet velocity  $\geq 2.7$  m/s (peak instantaneous gradient  $\geq 30$  mmHg) measured by CW Doppler under basal (resting) conditions or physiologically provoked (Valsalva maneuver or post premature ventricular contraction) AND
  - An increment in peak LVOT gradient  $\geq 10$  mm Hg from baseline
  - Additional notes and considerations:
    - LVOT obstruction will be considered severe if peak LVOT jet velocity  $\geq 3.5$  m/s (peak instantaneous gradient  $\geq 50$  mm Hg).
    - **Non-severe:** Peak LVOT jet velocity greater than or equal to 2.7 ms/s to 3.4 m/s (peak instantaneous gradient  $\geq 30$  mm Hg)
    - **Non-event:** Less than 2.7 m/s peak LVOT jet velocity
    - All cases with peak LVOT jet velocity  $\geq 2.7$  m/s (peak instantaneous gradient  $\geq 30$  mm Hg) measured by CW Doppler will be submitted to the CEC for adjudication.
    - AEs/SAEs related to *intraprocedural* increase in LVOT gradient will be submitted to the CEC for adjudication. Cases of intraprocedural LVOTO resulting into death or explant will be considered severe LVOTO.
    - Cases of LVOTO resulting into septal reduction therapy (alcohol septal ablation or septal myectomy) will be considered severe LVOTO.
    - Cases of LVOTO incidentally discovered by pathology will be assessed based on the last available peak LVOT jet velocity measured by CW Doppler; any attempt should be done to submit this last echo to the Echo Core Lab and to the CEC. Alternatively, the last follow-up echo Core Lab CW measurements will be used to define LVOTO.

Outflow Tract Gradient Severity Scale CW Doppler			
	Mild	Moderate	Severe
Velocity m/sec	$\geq 2.7$ -3.1	3.2 - 3.4	$\geq 3.5$
Peak Gradient mmHg	$\geq 30$ -39	40 - 49	$\geq 50$

- Aortic valve regurgitation ( $\geq$  moderate or 2+)
- Other

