## **Appendix B: Participant Information and Consent Form**

## **Appendix C: Instructions for Use**

## Appendix D: Endpoint Definitions

Analysis of study results will include the following additional MVARC defined exploratory endpoints:

**Technical Success** (measures at exit from catheterization laboratory)

All of the following must be present:

- I. Absence of procedural mortality; and
- II. Successful access, delivery, and retrieval of the device delivery system; and
- III. Successful deployment and correct positioning of the first intended device; and
- IV. Freedom from emergency surgery or reintervention related to the device or access procedure

**Device Success** (measured at 30 days and at all later post-procedural intervals):

All of the following must be present:

- I. Absence of procedural mortality or stroke; and
- II. Proper placement and positioning of the device; and
- III. Freedom from unplanned surgical or interventional procedures related to the device or access procedure; and
- IV. Continued intended safety and performance of the device, including:
  - a. No evidence of structural or functional failure
  - b. No specific device-related technical failure issues and complications
  - c. Reduction of MR to either optimal or acceptable levels without significant mitral stenosis (i.e., post-procedure EROA is 1.5 cm^2 with a transmural gradient <5 mm Hg), and with no greater than mild (1+) paravalvular MR (and without associated hemolysis)

**Procedural Success** (measured at 30 days)

All of the following must be present:

- I. Device success (either optimal or acceptable), and
- II. Absence of major device or procedure related serious adverse event, including:
  - a. Death
  - b. Stroke
  - c. Life-threatening bleeding (MVARC scale)
  - d. Major vascular complications
  - e. Major cardiac structural complications
  - f. Stage 2 or 3 acute kidney injury (includes new dialysis)
  - g. Myocardial infarction or coronary ischemia requiring PCI or CABG
  - h. Severe hypotension, heart failure, or respiratory failure requiring intravenous pressors or invasive or mechanical heart failure treatments such as ultrafiltration or hemodynamic assist devices, including intra-aortic balloon pumps or left ventricular or biventricular assist devices, or prolonged intubation for 48 h
  - i. Any valve-related dysfunction, migration, thrombosis, or other complication requiring surgery or repeat intervention

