#### Analysis Method:

Number and percentage of subjects with no significant MV stenosis at each visit will be calculated as appropriate by definition. Statistics summarizing the distributions of the component endpoints (number and percentage of subjects with MV mean gradient  $\leq 5$  mmHg and  $< 10$  mmHg, number and percentage of subjects with EOA  $\geq 1.5$  cm $^2$ ) will also be presented.

- LVOT patency (measured by echo through 30 days post-procedure)

Hypothesis/Decision Criteria:

No specific hypotheses or pass/fail criteria have been set. The analysis will be descriptive and no statistical hypothesis tests are planned.

Endpoint Definition/Parameters to Be Estimated:

This endpoint is defined using variables on the core lab echo CRF.

LVOT patency is defined as not having an LVOT obstruction. LVOT obstruction is defined as having peak LVOT jet velocity  $\geq 2.7$  m/s (peak instantaneous gradient  $\geq 30$  mmHg) measured by CW Doppler under basal (resting) conditions or physiologically provoked (Valsalva maneuver or post premature ventricular contraction) and having an increment in peak LVOT gradient  $\geq 10$  mmHg from baseline.

Data Collection and Analysis Dataset:

Data will be collected on the core lab echo CRF (either TTE or TTE data, whichever demonstrates a higher degree of LVOT obstruction (equivalent to lowest degree of patency), will be used). Analysis dataset is the Implanted Subjects analysis set.

Analysis Method:

Number and percentage of subjects with LVOT patency at each visit will be calculated. Statistics summarizing the distributions of the component endpoints (number and percentage of subjects with peak instantaneous gradient  $\geq 30$  mmHg, and number and percentage of subjects with an increment in peak LVOT gradient  $\geq 10$  mmHg from baseline) will also be presented.

- Improvement of NYHA Class from baseline (through 30 days post-procedure)

Hypothesis/Decision Criteria:

No specific hypotheses or pass/fail criteria have been set. The analysis will be descriptive and no statistical hypothesis tests are planned.

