#### Endpoint Definition/Parameters to Be Estimated:

This endpoint is defined using variables on the AE, procedure and core lab echo CRFs.

Device success is measured at discharge, 30 days and at all later post-procedure intervals. All of the following must be present:

- Absence of procedural mortality or stroke (free from death and stroke within 30 days of procedure, AE CRF); and
- Proper placement and positioning of the device (TMVR implanted is "Yes", procedure CRF); and
- Freedom from unplanned surgical or interventional procedures related to the device or access procedure (Conversion to open MV replacement is "No" and Other repair surgery is "No", procedure CRF); and
- Continued intended safety and performance of the device, including
  - o No evidence of structural or functional failure (free from AEs for device malfunction for structural or functional failures, and free from explant and MV reinterventions, AE CRF)
    - Delivery failure (i.e., technical failure)
    - Structural failure
    - Functional failure
  - o No specific device-related technical failure issues and complications (core lab echo, AE, procedure CRF)
    - Paravalvular leak (core lab echo, AE CRF)
      - Major/Minor: Having a major paravalvular leak is considered as having a device failure.
    - Coronary vessel compression or obstruction (defined using CEC code, AE CRF)
      - Major/Minor: Having a major coronary vessel compression or obstruction is considered as having a device failure.
      - Symptomatic/Not symptomatic: Having a symptomatic coronary vessel compression or obstruction is considered as having a device failure.

- Requiring treatment/Not requiring treatment: Having a coronary vessel compression or obstruction requiring treatment is considered as having a device failure.
- Transient/Persistent: Having a persistent coronary vessel compression or obstruction is considered as having a device failure.
- Pericardial effusion (defined using CEC code, AE CRF)
  - Major/Minor: Having a major pericardial effusion is considered as having a device failure.
- Conversion to open mitral valve surgery during a transcatheter procedure (Conversion to open MV replacement is "No", procedure CRF)
- Device malpositioning (defined using CEC code, AE CRF)
- Device detachment (defined using CEC code, AE CRF)
  - Partial/Complete: Having a complete device detachment is considered as having a device failure.
- Device fracture (defined using CEC code, AE CRF)

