  - Major/Minor: Having a major device fracture is considered as having a device failure.
- Damage to the native mitral valve apparatus (defined using CEC code, AE CRF)
- Interaction with non-mitral valve intracardiac structures (defined using CEC code, AE CRF)
- Device thrombosis (defined using CEC code, AE CRF)
  - Major/Minor: Having a major device thrombosis is considered as having a device failure.
- Endocarditis (defined using CEC code, AE CRF)
- Haemolysis (defined using CEC code, AE CRF)

- Reduction of MR to either optimal (post-procedure MR reduced to 0+ to trace, with no more than 1+ paravalvular MR) or acceptable (post-procedure MR reduced by at least 1 grade from baseline and to 1+ to 2+ with no more than

1+ paravalvular MR) levels without significant mitral stenosis (i.e., post-procedure EOA is  $\geq 1.5 \text{ cm}^2$  with a transmtral gradient  $< 5 \text{ mmHg}$ ) and with no greater than mild (1+) paravalvular MR (and without associated hemolysis) (core lab echo CRF)

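### SAP device success takes no core-lab echo input for LVOT obstruction, so a subject can fail LVOT patency and still count as a device success at the same visit

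*Combined protocol and SAP*

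**What the plan says.** **LVOT patency (SAP 7.9.2, continued through 5 years in 7.9.3).** The source is the core lab echo form. "LVOT patency is defined as not having an LVOT obstruction", and obstruction needs both a peak jet velocity of at least 2.7 m/s (30 mmHg) and a rise in peak gradient of at least 10 mmHg over baseline. "Number and percentage of subjects with LVOT patency at each visit will be calculated".

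**Device success (SAP 7.9.3).** "Device success is measured at discharge, 30 days and at all later post-procedure intervals". Among its conditions, CIP-1403 Appendix D lists "No specific device-related technical failure issues and complications". The SAP breaks that condition into items, and LVOT obstruction is not named in any of them. The nearest reads "Interaction with non-mitral valve intracardiac structures (defined using CEC code, AE CRF", with no echo source. Another item in the same list does have one: "Paravalvular leak (core lab echo, AE CRF". The MR-reduction and mitral-stenosis component is also read from the core lab echo.

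**CEC (SAP 5.3, repeated in 7.10).** "The CEC will adjudicate all deaths, serious adverse events (SAEs), and safety endpoint events reported by the investigators". SAP 7.9.1 adds that adverse events come from sites and that CEC review of them is possible rather than certain.

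**Transseptal CIP, 17.1.27.** This section, in a different study's plan, places LVOT obstruction within the interaction category. It also has an echo-triggered referral: the sentence opening "All cases with peak LVOT jet velocity" sends every CW Doppler case at or above 2.7 m/s to the CEC. SAP section 3 lists only CIP-1403 versions as its basis.

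**The concern.** Two endpoints in one report describe the same anatomical outcome from different sources, and no rule connects them. An obstruction measured centrally without symptoms need not become a site-reported adverse event. Without an event there may be nothing for the CEC to code. LVOT patency then records a failure while device success records none.

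LVOT obstruction is a named device risk in CIP-1403 section 5.2, and freedom from it is a secondary performance endpoint. A composite meant to capture device-specific technical failure should not be able to miss it when the measurement is already on file. The gap also carries into procedural success (30 days) and individual subject success (1 year), because both require device success.

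**Working it through.** The plan states no figure for this point, and the study has no hypothesis test or derived sample size. The check is therefore mainly logical.

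**Step 1: can one subject appear in both results?** LVOT patency uses the Implanted set and device success uses the Attempted set. SAP 7.1.3 draws implanted subjects from attempted subjects, so every subject assessed for patency also belongs to the device-success set. The visits overlap as well (discharge, 30 days and later).

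**Step 2: compare the outcomes.** Take a subject who meets both 7.9.2 echo criteria and passes every other device-success component. For the referred cases, assume the CEC applies the transseptal 17.1.27 definition, which also requires visible narrowing of the outflow tract. SAP 7.9.2 has no such requirement.

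| Route to the CEC | Visible narrowing | LVOT patency | CEC code | Device success | Agree? |
|---|---|---|---|---|---|
| None | either | fail | no | success | no |
| Echo-triggered referral | absent | fail | no | success | no |
| Echo-triggered referral | present | fail | yes | failure | yes |

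The first row is open under the SAP text. The second shows that importing the transseptal referral rule would narrow the gap without closing it.

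**Step 3: check the threshold pair.** With gradient = 4v², 4 × 2.7² = 29.2 mmHg, consistent with the stated 30 mmHg after rounding. The disagreement does not come from mismatched cut-offs.

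**Step 4: direction.** Adding an echo criterion joined by OR can only turn a success into a failure, or bring into the denominator, as a failure, a subject previously left out for missing data. Either change lowers the rate or leaves it at zero. Omitting the criterion therefore cannot work against the device.

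**Step 5: size per subject.** Rescoring k subjects from success to failure lowers the rate by k/n. SAP section 6 gives a ceiling of 95 treated subjects, so 1/95 = 1.05 points each. At n = 50 it is 1/50 = 2.0 points.

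For illustration only, with both the base rate and k assumed (n = 95, exact 95% intervals):

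| Assumed device success | k = 3 rescored | k = 5 rescored |
|---|---|---|
| 57/95 = 60.0% (49.4 to 69.9) | 54/95 = 56.8% (46.3 to 67.0) | 52/95 = 54.7% (44.2 to 65.0) |
| 76/95 = 80.0% (70.5 to 87.5) | 73/95 = 76.8% (67.1 to 84.9) | 71/95 = 74.7% (64.8 to 83.1) |

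The shifts are 3/95 = 3.2 and 5/95 = 5.3 points.

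**The case against.** The strongest reply is that the transseptal CIP cannot be used by halves. It is the only text that files LVOT obstruction under the interaction item, and it also refers every case above the velocity cut to the CEC. If it governs, most of the gap closes. If it does not, nothing places LVOT obstruction in that item. This stands as a caution, but it does not remove the point. If LVOT obstruction lies outside the interaction item, no device-success item names it. If it lies inside, the SAP still does not adopt the referral rule, and the narrowing condition leaves room for disagreement.

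A reader might infer that the CEC sees nothing except what investigators report. The SAP says what the committee will adjudicate; it does not say it sees nothing else. Several device-success items expect CEC codes for minor as well as major events, which suggests a wider remit. The CEC charter, which the SAP version history mentions, is not available and may hold a referral rule.

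A reader might also infer that the sponsor took the transseptal definition and dropped its referral clause. The version history says only that the LVOT patency definition was aligned with current mitral studies. It names no source, and the SAP wording differs from 17.1.27.

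Sites also review echo and adverse events at each visit under CIP-1403 section 4.6, so some obstructions would be reported. LVOT patency and its components are tabulated separately, and case summaries go to FDA, so the finding would not be hidden. Both points reduce the consequence, but neither corrects the composite.

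**Conclusion.** The concern holds in a limited form. As written, device success has no core-lab input for LVOT obstruction, and neither the SAP nor CIP-1403 supplies a route from the core lab to the CEC. A subject with a core-lab obstruction and no CEC code is a patency failure and, if all else passes, a device success at that visit.

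It would go too far to say that such a subject therefore passes procedural success and individual subject success. Device success is necessary for both but not sufficient. Procedural success also fails on, for example, heart failure needing mechanical support or valve complications needing reintervention, and device success itself fails on explant or mitral reintervention. What remains is mainly obstruction seen on echo without such consequences. For that subject, the obstruction does not count against the device-success requirement inside the other two composites.

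The bias runs one way and its size is unknown. The 1.05 points per subject assumes a denominator of 95, which is an enrolment ceiling; the actual denominator is subjects with full success or at least one failure. The documents give no count of discordant subjects and no expected success rate. The affected composites are exploratory, without pass or fail criteria, and the primary safety endpoint is untouched. It is still worth correcting, because the change is cheap and removes a possible contradiction within one report.

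**What to change.** In SAP 7.9.3, device success, reword the interaction item so that it is a failure if CEC-coded, or if the core lab echo at that visit meets the LVOT obstruction definition in 7.9.2. Name the core lab echo as a source, as the paravalvular leak item does. Do not carry a finding forward from earlier visits: the leak item states no carry-forward, and because 7.9.2 accepts provoked gradients, a single early reading would otherwise mark a subject as a failure at every later visit.

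Report the CEC-coded-only result beside the new one, so that the contribution of echo-only findings is visible. It would also help if SAP 5.3 stated whether core-lab LVOT findings are referred to the CEC.

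The cost is one sentence and a merge of core-lab data already collected. The reported success rate may be slightly lower, and an echo-only finding can count as a failure without adjudication. The side-by-side result addresses the second of these.
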